Those randomized to the will receive either 40mg of a non-fluorinated injectable glucocorticoid, methylprednisolone acetate (1cc) combined with 1cc of 1% Lidocaine or 1cc f1% Lidocaine plus 1cc of normal saline. The injection will be performed unilaterally if pain is single sided or bilaterally if the pain is in both sacroiliac joint regions The injection will be ultrasound guided and performed by the PI [name] who is trained in musculoskeletal ultrasound and ligamentous injections as a specialist in physical medicine and rehabilitation. [name] and the participant will both be blinded to the type of injectate used. Study visits 2 and 3 will include the same questionnaires and physical examination and will document any change in the pregnancy status. Study visit 4 will occur 6 weeks post-delivery and will include the same questionnaires and physical examination to determine if any chronic pain remains. Patients will be allowed to utilize acetaminophen as needed and the amount utilized in each intervention arm will be recorded. Total study visit time is expected to be 60 minutes for study visit 1 and 30 minutes for visits 2-4. Standard physical examination maneuvers validated for the assessment Protocol Version 4 – 03-06-2015

of pregnancy related PGP will be performed by the PI [name] and include pelvic pain provocation tests and functional stability testing. It will be noted with each maneuver whether the test was positive or negative. They will include:

a. *Patrick's Faber test*: With the patient in supine, the patient's leg is flexed, abducted and externally rotated so that the heel rests on the opposite kneecap. This test is positive with production of pain in the sacroiliac joint.

b. *Posterior Pelvic Pain Provocation (P4) test*: with the patient supine, the femur is flexed to be perpendicular with the table at 90 degrees and the knee is flexed at 90 degrees. A gentle force is applied to the femur in the direction of the examination table. The test is positive when the patient experiences pain in the gluteal region of that leg.

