c. *Long Dorsal Sacroiliac Ligament (LDL) palpation test*: The subject lies on her side with slight flexion in both hip and knee joints. Specifically, the LDL is palpated directly caudomedially from the posterior iliac spine to the lateral dorsal border of the sacrum if palpation causes pain that persists five seconds after removal of the examiner's hand, it is recorded as pain. If the pain disappears within five seconds, it is recorded as tenderness. When the identical pain is felt directly in the vicinity, but outside the borders of the ligament, the test is not deemed as positive.

d. *Pubic Symphysis palpation test*: Examiners will palpate the subject's pubic symphysis joint while the patient is lying supine for tenderness. If palpation causes pain that persists five seconds after removal of the examiner's hand, it is recorded as pain. If the pain disappears within five seconds, it is recorded as tenderness.

e. *Modified Trendelenburg's test*: The standing woman stands on one leg and flexes the other at 90° (hip and knee). The test is considered positive if pain is experienced in the symphysis.

f. *Active Straight Leg Raise (ASLR) test*: performed with the patient supine with straight legs extended on the table 20 cm apart. The patient raises each leg one at a time 20 cm above the table without bending the knee. A) The test is positive when the patient describes a heaviness or difficulty in performing the task. B) In the second part of the maneuver, posterior

compression is applied and the patient is then asked to actively perform a straight leg raise. If there is greater ease in lifting the leg this is considered a positive test. The patient will be asked to score impairment (scoring inadequacy to raise the legs but not pain) on a 6-point scale: not difficult at all = 0, minimally difficult = 1, somewhat difficult = 2, fairly difficult = 3, very difficult = 4, unable to do = 5, the scores of both sides will be added so that the summed score can range from 0-10. Impairment is considered severe if the summed bilateral score is at least 4.

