3.8 Analysis

Data will be analyzed using descriptive univariate statistics with STATA 11.0. In this population, there is evidence from current literature that pain and disability may not be normally distributed. If this is the case, the primary and secondary outcomes, pain and disability respectively, will be presented as median values and interquartile ranges. Comparisons between the intervention groups at follow-up will be performed using the Mann Whitney U test and change within groups from baseline to follow-up will be examined using the Wilcoxon signed-rank test. If data are sufficiently normally distributed and differences are found, multivariate analyses will be conducted. This will determine the need to control for group differences based on location of pain, history of low back pain or pelvic girdle pain, age, educational level, parity, and time from pain onset. Additional secondary analyses will examine the impact of the treatment group assignment on physical examination tests using chi-square test of proportions.

4. Risks and Benefits

The excellent overall safety and efficacy record of injectable corticosteroids is well established²⁶. A prospective evaluation of intraarticular and periarticular injections with methylprednisolone found a very low rate of complications²⁷. Systemic effects of injectable corticosteroids are influenced by the agent used, dose, frequency and number of sites injected. Osteoporosis is found only with use of systemic/oral steroids and myopathy more commonly documented with oral fluorinated steroid use has not been reported with intraarticular injections. The ability of intraarticular injections to suppress the hypothalamic-pituitary-adrenal (HPA) axis

Protocol Version 4 – 03-06-2015

is well documented²⁸ but has not been described with extraarticular or ligamentous injections. A corticosteroid induced increase in glucose synthesis is not seen in soft-tissue injections of methylprednisolone acetate²⁹.

Fetal Risk and Benefit

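### The ASLR outcome has two unreconciled rules for a positive test plus a severity cut, and the 0-10 score collected for it has no stated analysis

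*Combined protocol and SAP*

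**What the plan says.** ASLR is one of six examination tests listed as secondary outcomes in section 1.2, which gives no scale or positivity rule for it. The definition is in section 3 (Protocol), item f, and has three elements.

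- Part A, the unassisted raise: "The test is positive when the patient describes a heaviness or difficulty in performing the task".
- Part B, the raise under posterior compression: "If there is greater ease in lifting the leg this is considered a positive test".
- A difficulty score of 0 to 5 per side: "the scores of both sides will be added so that the summed score can range from 0-10", with the cut "Impairment is considered severe if the summed bilateral score is at least 4".

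The paragraph introducing the tests asks for a binary record: "It will be noted with each maneuver whether the test was positive or negative". Section 3.8 then plans to examine "the impact of the treatment group assignment on physical examination tests using chi-square test of proportions". The rank-based description in the same section covers pain and disability: "the primary and secondary outcomes, pain and disability respectively, will be presented as median values and interquartile ranges". The ASLR score is not mentioned there. Section 3.1 also uses ASLR positivity, judged on the symptomatic side, as one of the four tests of which two must be positive for entry.

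**The concern.** Three different yes/no results can be read from item f (A, B, severe), as can combinations of A and B, and the plan does not choose. Section 1.2 asks whether the physical examination improves, so the coding decides what improvement on ASLR means. Some codings are insensitive and some can move in the wrong direction for some women. With none fixed in advance, the choice could be made after the data are seen. The measure that avoids these problems, the 0-10 sum, is collected but no comparison of it is planned.

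**Working it through.** **1. Can A and B disagree?** For one side, let s be the difficulty score without compression and c the score with it, each 0 to 5. Take A positive as s ≥ 1 and B positive as c < s, and assume compression never makes the raise harder (c ≤ s). That leaves 1+2+3+4+5+6 = 21 states:

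- A+/B+ (c < s): 1+2+3+4+5 = 15
- A+/B− (c = s ≥ 1, difficulty not eased): 5
- A−/B− (s = c = 0): 1
- A−/B+: none

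So they can disagree, in one direction only.

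**2. What does a change from positive to negative mean?**

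- Under A there are 20 × 1 = 20 such changes, all to s = 0, so the unassisted score never worsens. A-or-B gives the same result, because B+ implies A+ here.
- Under B there are 15 × 6 = 90. A woman starting at s has s possible values of c and ends at s = c = t. The unassisted score is worse (t > s) in Σ s(5−s) = 4+6+6+4+0 = 20, unchanged in Σ s = 15, and better in Σ s² = 1+4+9+16+25 = 55. A-and-B gives the same counts.

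Example: a score of 3 eased to 1 at baseline is B+. A later score of 5 with no easing is B−, while A stays positive. These are counts of possible states, not expected frequencies.

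**3. Part A and the severe cut.** A fall from 5+5 = 10 to 1+1 = 2 leaves A positive on both sides. Of the 36 pairs of left and right scores, 35 have some difficulty on at least one side. Ten sum to 3 or less (1+2+3+4), so 36 − 10 = 26 are severe, and 35 − 26 = 9 are positive under A but not severe.

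**4. The plan's own sample size.** There is no figure for ASLR. For the NRS, the Appendix II formula with Δ = 2 and σ = 2.5 (25 mm) gives n = (3.96 × 2.5/2)² = 24.5, so 25 per group. This reproduces the plan.

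**5. Cost of dichotomising.** The documents give no ASLR mean, SD or effect. Assumptions: normal scores rounded and clipped to 0-10, a 2-point benefit applied before clipping, 25 per group, two-sided 5%. Score ≥ 1 stands in for part A. With 4,000 simulated trials per scenario, the standard error is at most 0.5/√4000 = 0.8 percentage points. At SD 2.5:

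| Control mean | Mann-Whitney on score | Chi-square, ≥ 1 | Chi-square, ≥ 4 |
|---|---|---|---|
| 4 | 76% | 46% | 65% |
| 5 | 76% | 31% | 64% |
| 6 | 78% | 10% | 56% |

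Over the wider grid (control mean 2-6, SD 2-3; 15 scenarios) the ranges are about 54-92% on the score, 1-82% on any difficulty and 37-82% on severe. The score had more power than either cut in all 15.

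**6. Closed-form check.** Cutting an unclipped normal score midway between the arm means (Δ = 2, SD 2.5) gives proportions Φ(0.4) = 0.655 and 0.345. For 80% power, n = [1.96√(2 × 0.5 × 0.5) + 0.84√(0.655 × 0.345 × 2)]² / 0.311² ≈ 40 per group, against 25 on the score. With 25 per group, power is 60%.

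**The case against.** A reader might infer that the plan scores worsening as improvement. The documents do not support that. Item f presents B as the second part of one manoeuvre and never says that it decides the result. The reversal needs B alone or A-and-B; under A or A-or-B it cannot occur. B also turns negative when the difficulty disappears, which is true improvement. What stands is that the reversal is possible for some women under readings the text does not exclude.

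A reader might also infer that the ASLR result is almost unable to change. That follows only if part A is used and the control mean is high: the 1% figure arises at mean 6, SD 2. With control means of 2 to 3.5 and SD 2 to 2.5, any difficulty has about 51-81% power against 72-91% for the score. Low means are plausible, since both arms receive four weeks of physical therapy and pain may be one-sided. They are assumptions too. The score still does better.

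A binary examination result is a legitimate secondary endpoint. If the severe cut was intended, the loss is the ordinary price of dichotomising. But the plan does not say that this cut is the one tested.

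It is tempting to extend the point to palpation of the long dorsal ligament and the symphysis. Those tests have no conflicting rules and no reversal, and their pain and tenderness grades are recorded.

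Finally, ASLR is one of six examination tests in an additional secondary analysis. That limits the weight of the point without removing it.

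**Conclusion.** The point holds as an unresolved outcome definition and an omitted analysis. Item f supplies two positive rules and a severity cut, the plan reduces them to one yes/no result without saying how, and the directional 0-10 score has no stated comparison. That part rests on the text alone. The size of the power loss rests on assumed ASLR values: the direction was the same in every scenario tried, but the amount ranges from small to nearly total. The state counts show that reversal is possible under B or A-and-B, not how often it would happen.

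The same ambiguity reaches eligibility, where positivity is judged on the symptomatic side while the score sums both sides. The documents give no ground for preferring A, B or a combination for entry, and none is preferred here. The primary NRS outcome and its 25 per group are unaffected. This should be corrected, but it does not threaten the trial's main conclusion.

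**What to change.** - Make the 0-10 summed score the ASLR outcome. State that it refers to the raise without compression: it is read that way here, but item f places the scoring sentence straight after part B.
- Compare arms on that score with the Mann-Whitney test that section 3.8 already gives for pain and disability.
- Report part B descriptively.
- Reconcile the positivity rules into one stated rule for the eligibility count in section 3.1. The choice is the sponsor's.
- Optionally, analyse the two palpation tests by ordered grade (none, tenderness, pain).

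The cost is wording in section 3, section 3.1 and section 3.8. The score is already collected, so no visit, test or participant is added.

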2.1 Research to date

Randomized clinical trials on exercise/physical therapy interventions^{12,13}, acupuncture¹⁴ and an educational intervention^{15,16} have been performed in the study of PGP during pregnancy. There are currently no randomized clinical trials, however, evaluating the use of pain medications or corticosteroids for PGP in pregnancy. Torstensson et al performed a randomized double blind controlled trial evaluating the use of intravaginal corticosteroid injection at the ischiadic spine in postpartum women with persistent sacral pain. Slow release triamcinolone and lidocaine provided superior pain relief compared with saline and lidocaine alone.¹⁷ Musculoskeletal ultrasound (US) has been widely utilized in other musculoskeletal joint disorders to diagnose pathology¹⁸ and recently to identify the posterior sacroiliac joint ligamentous structures¹⁹. It has also been used to evaluate the sacroiliac joint in the non-

pregnant state for the purpose of diagnostic (anesthetic) joint injection with good success²⁰. US is already routinely being performed for obstetrical use during pregnancy and is considered safe in pregnancy due to its lack of radiation exposure²¹.

Glucocorticoids constitute one of the most frequently prescribed medications during pregnancy, used commonly in preeclampsia and for maternal inflammatory, dermatologic, and autoimmune disorders. Antenatal glucocorticoids are used for a multitude of reasons in pregnancy. Examples of use are asthma refractory to inhalant therapy (*National Asthma Education and Prevention Program: Full Report of the Expert Panel: Managing asthma during pregnancy: Recommendations for pharmacologic treatment – 2004 update. NHLBI, NIH publication no. 005-3279I*), autoimmune disorders^{22,23} and for acceleration of fetal lung maturity for women at risk of preterm birth²⁴.

Although fluorinated glucocorticoids are known to cross the placenta readily, the majority of prednisone and methylprednisolone (non-fluorinated glucocorticoids) are inactivated in the placenta and do not reach the fetus in significant concentrations. Both of the latter are Category C agents in that animal studies show no risk but no definitive studies in humans have been done, and may be safely used as anti-inflammatory/immunosuppressive agents if indicated in pregnancy²⁵.

3. Protocol (See Appendix II and III)

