Personal Health Information to be collected The personal health information (PHI) items that will be collected during pregnancy will include: name, phone number; date of birth; BMI; height; age; race; education level; income level; number of previous pregnancies; number of previous deliveries; types of previous deliveries, past abdominal surgeries if any, current medications; history of other pain diagnoses, history of depression; history of neurological disease; history of anxiety; history of sexual abuse; previous low back injury; previous low back or pelvic pain; history of smoking; history of infertility; history of urinary or fecal incontinence; history of interstitial cystitis; history of arthritic conditions (osteoarthritis, rheumatoid arthritis, lupus); body parts affected by arthritic conditions; diabetes (Type I, Type II, gestational); gestational week of current pregnancy; due date of current pregnancy; number of babies expected; trimester/gestational week of onset of low back and/or pelvic pain (if applicable); current pregnancy complications; occurrence of miscarriage; activity and exercise types and levels during pregnancy; activity level restrictions; and duration for any previous physical therapy; previous home exercise program; and physical therapy descriptions and reasons for initiating therapy after enrollment in the study. Social history including marital status, support at home, and type of occupation will be documented.

3.1 Eligibility criteria:

- English speaking pregnant women presenting in their second or third trimester with posterior PGP. Trimester will be determined from date of last menses or ultrasound date.

- Women who have failed physical therapy for pain management (physical therapy, chiropractic management, aquatic therapy)
- Pain NRS on average of greater than or equal to 5/10 at Visit 1
- Pain must be between the upper level of the iliac crests and the gluteal folds in conjunction with or separately from pain in the pubic symphysis and influenced by position and locomotion
- 2/4 positive physical examination tests on the symptomatic side including the P4 test, the LDL test, pubic symphysis palpation and the ASLR

3.2 Exclusion criteria:

- Non-English speaking pregnant women <21 or >50 years old
- Women presenting with PGP in the first trimester (<13 weeks gestation)
- Women with pubic symphysis (anterior) pain alone
- Women who have not yet received some form of physical therapy for their pain

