- Pain above the upper level of the iliac crest
- History of lumbar or pelvic fracture, neoplasm, inflammatory disease, active urogenital infection or active gastrointestinal illness, current physical therapy or other therapies for PGP, or previous surgery of the lumbar spine, pelvic girdle, hip joint or femur
- History or signs of radiculopathy or other systemic neurologic disease
- Women with diabetes or gestational diabetes

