3.5.1 Pre-Enrollment

Protocol Version 4 – 03-06-2015

Eligible participants will be informed about this trial during any second or third trimester visit when they complain or present clinically with PGP in the office. Special efforts will be made to increase enrollment in certain subgroups (minorities). No other medical or other documentation will be required for determining eligibility. After assuring eligibility, patients may proceed to study visit 1 where consent and randomization will take place. With prevalence rates of PGP in pregnancy at 45%, there will be ample availability of eligible participants. Sixty total participants will be enrolled.

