treatment outweighs the minimal risk. Both study groups will receive standard of care physical therapy (cost covered by their insurance), a proven treatment for pregnancy related pelvic girdle pain. For the intervention group that receives methylprednisolone, expected immediate side effects might include vasovagal reaction and delayed (2 days) side effects might include injection site soreness, sweating or facial flushing³⁰. Toxicity at high levels and multiple dosing effects are not expected given that this is a low dose of corticosteroid injected locally. Infection rates associated with injection are low and typically seen in intraarticular not extraarticular injections³¹. A possible rare adverse effect might include allergic reaction. If an adverse reaction or side effect occurs, the subject will be seen by [name] (maternal fetal medicine) at Loyola. This will also be immediately reported to the IRB.

The benefits of the intervention include the possibility of superior pain relief compared with placebo. Lidocaine has been safely and successfully used in pregnant women undergoing amniocentesis.³² Oral steroids are used for other conditions in pregnancy such as asthma, rheumatoid arthritis, and severe sinusitis. They are also utilized in the treatment of pre-term labor to assist in the development of fetal lung maturity. Methylprednisolone is a class B drug and its well-established clinical utility in other diseases lends to the safety of its potential use in this debilitating pain condition (PGP) in pregnancy and warrants further study for the treatment of musculoskeletal pain.

I. Safety Monitoring Plan

a. Definition of adverse events, serious adverse events

- i. An adverse event is defined as any symptom or medical problem experienced by the participant following consent to participate. All adverse events must be reported to the study physician and regulatory coordinator within three working days of discovery. All adverse events that occur during the trial will be recorded on the adverse event log. The investigator study physician will ask patients at each visit "Have you experienced any

symptoms or medical problems since your last visit?” and will subsequently record all events using the adverse event log.

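### The exclusions do not address corticosteroids taken for reasons other than inflammatory disease or PGP, so background steroid use could modestly dilute the contrast under test

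*Combined protocol and SAP*

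**What the plan says.** The arms are meant to differ in one ingredient, methylprednisolone acetate (section 3.3), and section 1.1 presents the trial as a way to learn how far inflammation contributes to PGP.

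Neither section 3.1 nor section 3.2 mentions current or recent corticosteroid use by any route. The two exclusions that come closest are "History of lumbar or pelvic fracture, neoplasm, inflammatory disease, active urogenital infection or active gastrointestinal illness, current physical therapy or other therapies for PGP" and "Women with diabetes or gestational diabetes".

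The protocol also describes the drug class as common in this population. Section 2.1, repeated in section 4, states: "Glucocorticoids constitute one of the most frequently prescribed medications during pregnancy, used commonly in preeclampsia and for maternal inflammatory, dermatologic, and autoimmune disorders". It adds asthma, and use "for acceleration of fetal lung maturity for women at risk of preterm birth". The maternal risk text in section 4 says: "Oral steroids are used for other conditions in pregnancy such as asthma, rheumatoid arthritis, and severe sinusitis".

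The personal health items in section 3 include "current medications; history of other pain diagnoses", but no eligibility rule refers to them, and section 3.5.1 says "No other medical or other documentation will be required for determining eligibility". Section 3.5.2 stratifies on pain location only. The covariates listed in section 3.8 include no medication variable. The only rule on a concomitant drug concerns acetaminophen (section 3). The Safety Monitoring Plan provides a concomitant medication log, and no planned analysis uses it.

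**The concern.** A control woman taking a systemic steroid for another condition is not a clean no-steroid control, and a woman in the active arm who already takes one may gain less from the injection. Either would pull the observed difference towards zero. In a trial of 60, a null result would then be harder to read.

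The disease exclusions cannot prevent every case. Sinusitis and many dermatologic uses are not plainly inflammatory disease in the sense of section 3.2. A steroid given for preeclampsia or fetal lung maturation may be started after randomization, during follow-up.

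There is also an exposure question. Section 4 sets aside toxicity and multiple-dosing effects because the dose is low and local. That argument does not cover a woman who is taking another corticosteroid at the same time.

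**Working it through.** **Which users the exclusions reach**

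| Use named in the protocol | Reached by section 3.2? |
|---|---|
| Steroid given for PGP itself | Yes, if current (other therapies for PGP) |
| Rheumatoid arthritis, lupus, other autoimmune disease | Probably, but the term inflammatory disease is undefined and section 3 still collects arthritis and lupus history |
| Asthma | Unclear, for the same reason |
| Dermatologic disorders, severe sinusitis | Not plainly |
| Preeclampsia, fetal lung maturation | No, and may arise after randomization |

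The gap is real but narrower than the whole drug class.

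**The plan's own sample size**

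Inputs from Appendix II: difference 2 NRS points, SD 25 mm (read as 2.5 points), two-sided alpha 0.05, power 80%. The stated formula, Δ/σ = 3.96/√n, gives n = (3.96 × 2.5 / 2)² = 24.5, so 25 per group. This reproduces. A noncentral-t calculation at 25 per group gives power of 79.1%.

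The plan enrolls 30 per group and expects 10% loss: 30 × 0.9 = 27 completers per group. At 27 per group, with no background steroid, t-test power is 82.2%. This is the fair starting point.

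**Dilution**

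Let q be the share of women exposed and g the fraction of the 2-point effect that they still gain. The average difference is 2 × (1 − q(1 − g)). Neither q nor g is in the documents, so a range is shown. Power is for a two-sample t test, SD 2.5, 27 per group.

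| q | Difference, g = 0 | Power, g = 0 | Difference, g = 0.5 | Power, g = 0.5 |
|---|---|---|---|---|
| 0% | 2.00 | 82.2% | 2.00 | 82.2% |
| 2% | 1.96 | 80.7% | 1.98 | 81.5% |
| 5% | 1.90 | 78.2% | 1.95 | 80.3% |
| 10% | 1.80 | 73.8% | 1.90 | 78.2% |

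Holding the SD at 2.5 is slightly favorable. If exposed controls score like treated women, the pooled SD at q = 10% rises to about 2.54. By the normal approximation at 25 per group, this takes power from 72.1% to 70.9%.

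**How many women**

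Expected exposed women among 60 are 60q: 1.2, 3 and 6. The chance of at least one is 1 − (1 − q)^60: 70% at 2% and 95% at 5%. Some exposure is likely even at low rates, but it may involve only a few women.

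**The case against.** The strongest reply is that the trial asks about a local, ultrasound-guided injection against a control injection, and background medication is equal across arms in expectation. Entry also requires average pain of at least 5/10 and failed physical therapy. A woman on a steroid who still qualifies has not been relieved by it, and nothing in the documents shows that a local injection would do nothing for her. On this view, accepting background medication under randomization is a legitimate choice.

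Much of this stands. The nil-gain case is a bound, not an estimate, which is why the half-effect column is shown. A reader might infer that steroid users bias the comparison, but the documents do not support that. Allocation is random and the effect is dilution, although chance imbalance is possible with 30 per arm and no stratification on medication. A reader might also infer that steroid users are admitted wholesale. Section 3.2 already removes part of the group.

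Nor can it be said that follow-up steroid use would be seen only in the safety log. Visits 2 and 3 repeat the questionnaires, and the study forms are not available to show whether medications are asked about again.

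The reply does not remove the silence itself. The plan neither accepts nor excludes background steroid use, and no listed analysis would show how much there was.

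**Conclusion.** The point holds in a limited form. Sections 3.1 and 3.2 leave open whether a woman taking a corticosteroid for another reason may enter, and section 3.8 would not detect the consequence. At 27 completers per arm and with no gain in exposed women, the power loss is about 1.5 percentage points at 2% exposure, 4 at 5% and 8.5 at 10%. With half the effect retained, the losses are about 1, 2 and 4 points.

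These figures rest on assumed exposure rates, an assumed gain in exposed women, and a t test standing in for the Mann-Whitney test that section 3.8 would use if scores are not normal. At 2% exposure the planned enrollment absorbs the loss. At 5% power is at or just below 80%, and at 10% it is below 80% in both cases. The documents do not support the inference that the trial is seriously underpowered for this reason.

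The added steroid exposure is a separate gap in the risk section. It cannot be quantified from the documents and is a matter for the investigators. Overall this is a cheap improvement, not a flaw that threatens the trial.

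**What to change.** - **Eligibility.** Add current or recent systemic or injected corticosteroid use to section 3.2, and check it at visit 1 against the current-medications item already collected. The investigators should set the look-back period. The 4 weeks in Appendix II describe when the injected drug is expected to act and should not be borrowed as a washout. State also what inflammatory disease covers.
- **Recording.** Create a flag for any non-study corticosteroid between randomization and the 4-week visit, taken from the existing medication log, and tabulate it by arm.
- **Analysis.** Keep the primary analysis in all randomized women. Add one sensitivity run of the same 4-week comparison without the flagged women. Label it supportive, because it drops women on a post-randomization event and may involve very few of them.
- **Risk text.** Have section 4 say whether concurrent steroid exposure was considered.

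The cost is one exclusion line, one derived variable, one table and one extra run. A few otherwise eligible women would be turned away. Steroids needed for clinical care are not restricted.
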